### 5.6 Other information to be collected

- Ordered HDMTX dose
- date/time of 24hr infusion start
- initial HDMT infusion rate with HDMTX concentration
- date/time of each change in HDMTX infusion rate and rate at which new infusion is set (if applicable)
- date/time of 24hr infusion start and stop for concomitant medications
- date/time of completion of HDMTX infusion
- toxicities experienced during infusion,
- hour at completion of monitoring
- total MTX given
- total leucovorin given
- all MTX levels resulted and time each MTX level was drawn.

## 5.7 After Treatment Adverse effects

Toxicities will be assessed until the next cycle of chemotherapy is administered or until 4 weeks after the administration of HDMTX, whichever time period is shorter. Each grade ≥3 adverse event will be collected for the following methotrexate related toxicities: mucositis, myelosuppression, hepatotoxicity (AST, ALT, GGT, bilirubin). All adverse events will be collected for neurotoxicity and nephrotoxicity. If multiple occurrences of a toxicity take place during a single course, please list a separate Max Grade This Occurrence for each occurrence.

The International Conference on Harmonization (ICH) Guideline for Good Clinical Practice E6(R1) defines an adverse event (AE) as:

"Any untoward medical occurrence in a patient or clinical investigation subject administered a pharmaceutical product and which does not necessarily have a causal relationship with this treatment. An AE can therefore, be any unfavorable and unintended sign (including an abnormal laboratory finding), symptom, or disease temporally associated with the use of a medicinal product, whether or not considered related to the medicinal product."

A Serious Adverse Event (SAE) is any AE that: 1. Results in death; 2. Is immediately life threatening; 3. Results in hospitalization – either initial or prolonged; 4. Results in persistent or significant disability/incapacity; 5. Results in congenital anomaly or birth defect; 6. Results in required intervention to prevent permanent impairment or damage or 7. Results in another serious

important medical event.

For the purposes of this study, it is not required to report SAEs which result in admissions to the hospital for simple febrile neutropenia or prolongation of a hospitalization secondary to delayed methotrexate clearance.

All SAEs should be identified and reported locally per institutional standards.

All unanticipated problems involving risks to subjects or others (UPIRSOs) should be identified and reported locally per institutional standards.

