The interventions in this protocol occur at the 2 and 6 hour (or 8 hour if the 2 hour level was  $\geq 100 \mu M$ ) time points. After the 24hr HDMTX infusion is complete, the individualized protocol will end and patients will remain on study but be off of the protocol therapy. After this time, management of MTX levels will continue according the treating physician's discretion using standard supportive care guidelines. This is elaborated below in Appendix B, suggested supportive care guidelines based on the COG algorithm. Interventions for toxicity are at the discretion of the treating provider as patients will be off treatment protocol at the 24hr time point. Glucarpidase should be administered based on the treating physician's discretion, with the recommendation that it be administered prior to the development of grade 4 nephrotoxicity and prior to 96 hours after the start of the HDMTX infusion. Administration of CPDG2 after these time points have been shown to be statistically associated with the development of  $\geq$  grade 4 toxicity.

Patients may be re-enrolled on this protocol therapy again for subsequent HDMTX infusions without the need for re-consent. In order to re-enroll, call the study coordinating center as outlined in Section 3.1 PRIOR to the cycle in which the dose modification protocol will be implemented.

The active length of study participation for each patient is 4 weeks after the last high-dose methotrexate infusion or until the next cycle of chemotherapy begins (which ever occurs first). Therefore, the maximum amount of active time on study would be 2.5 months. This would include 4 doses of HDMTX given every other week plus a 4 week follow-up period to assess for side effects.

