### 5.4 Laboratory Tests During Treatment

- Methotrexate levels and creatinine at times 2, 6 (or 8) and 24 hours are required for research purposes. Additional methotrexate levels and creatinine should be performed per institutional standards. Methotrexate levels and creatinine at hours 36 (if methotrexate levels are ≥150 micromolar), 42, 48 and every 6-12 hours thereafter until methotrexate is considered cleared (e.g. ≤0.4 micromolar at hour 48 and/or <0.1 micromolar thereafter) is highly recommended but considered optional. An example of routine post-methotrexate monitoring is outlined in Appendix B.

- The following labs should be drawn at Week 1 and Week 2 and repeated weekly until
  either the next dose of HDMTX is administered or 4 weeks have passed since the last
  dose of HDMTX: CBC, Creatinine, BUN, AST, ALT, total and direct bilirubin.

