- 1b) Explore potential changes in incidence of success (achieving an end infusion peripheral blood MTX concentration between 50-80  $\mu$ M) between sequential administrations of HDMTX. The primary endpoint and sample size calculation refer to the first cycle for each patient.
- Aim 2 2a) Calculate the frequency of adverse effects after each infusion. Success rate over multiple cycles within individual patients will be analyzed using generalized estimating equations for binary outcomes. This method will also be applied to the frequency of adverse events and to the assessment of factors associated with outcome. Continuous and ordinal/non-normal adverse effects will be compared via paired t-test or Wilcox sign rank test respectively.
- 2b) Describe the genotype of various methotrexate metabolizing SNPs in each subject. The polymorphisms of subjects in this study will be compared to published minor allele frequencies and when appropriate will be stratified by race/ethnicity. The purpose of this analysis will be to describe trends away from the major allele frequency in patients known to either have experienced or who are at high risk for developing adverse effects to HDMTX.
- 2c) Examine predictors of success of achieving a  $CP_{ss}$  of 50-80  $\mu$ M. Variables in our analysis will include (but not be limited to) age, sex, disease type, race/ethnicity and measure of pre-MTX renal function. An analysis both with and without SNP genotype will be performed secondary to the likelihood that race/SNP correlations will interfere with SNPs being a truly independent variable. We will initially use chi-square test for group variables and t-test for continuous variables. Logistic regression will be used for multivariable analysis to control for confounders and estimation of adjusted odds ratios. P<0.05 will be considered statistically significant.

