#### Analysis:

Aim 1a) Overall change in the incidence of success with the new protocol (achieving end infusion MTX levels  $50-80\mu M$ ) and

- 1b) change in incidence of success at various infusion times during interim maintenance and interim maintenance-like cycles in which patients are administered HDMTX every 2 weeks, as well as
- 1c) Success rate over multiple cycles within individual patients will be analyzed using generalized estimating equations for binary outcomes. This method will also be applied to the frequency of adverse events and to the assessment of factors associated with outcome. Continuous and ordinal/non-normal adverse effects will be compared via paired t-test or wilcox sign rank test respectively.

Aim 2) To examine predictors of success (achieving CPss of 50-80µM) we will initially use chi-square

test for grouped variable and t-test for continuous variables. Logistic regression will be used for multivariable analysis to control for confounders and estimation of adjusted odds ratios. P<.05 will be considered statistically significant.

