### **APPENDIX A**

Schedule of Assessments											
			Hours after methotrexate infusion Weeks starts (Week 0)								
Procedures	s	0	2	6 ¹	24	36‡	42‡	482‡	1	2 	Protocol section
Blood for SNP analysis		Х									5.5.2
Nuclear eGFR	Х										5.2
CBC with diff and platelets		Х							Х	Х	5.2
BUN		Х							Х	Х	5.2
AST/ALT/T&D* bilirubin		Х							Х	Х	5.2, 5.4
Creatinine		Х	Х	Х	Х	Х	Х	Х	Х	Х	5.4
Methotrexate level			Х	Х	Х	Х	Х	Х			4.1

S: Screening; Week 0: Week of high dose methotrexate administration; Hour 6 or 8 depending on 2 hour methotrexate level (Sec 4.1); ‡ highly recommended but optional; should be done per institutional standards of post-methotrexate monitoring;  Continue 48 hour labs per algorithm (recommended but optional) (See appendix B);  Repeat Week 2 labs weekly until the next dose of methotrexate or 30 days since last dose of methotrexate; \*T&D: Total and Direct

++ If the level is high at hour 36 or 42, but then the patient "catches up" and the level falls to the expected values of ≤1.0 and/or ≤ 0.4 μM at hours 42 and 48, respectively, resume standard leucovorin and hydration as long as urine output remains satisfactory.

Suggested post HDMTX infusion guidelines based on standard COG guidelines.

36 hr MTX level (if needed) +	42 hr MTX level	48 hr MTX level	Hydration and leucovorin rescue
>3 µM			Increase hydration to 200 mL/m²/hr
>10 µM			
 
Increase hydration to 200 mL/m²/hr.
 
Consider glucarpidase
 

	≤1.0 µM	≤ 0.4 µM	No further leucovorin after Hr 54, no further MTX levels after Hr 48
	1.01-9.9 µM	0.41-5.9 μM	Continue leucovorin at 15 mg/m² q 6 hours after Hr 54 until plasma MTX is < 0.1 μM
	40.40.0.14	0.00.11	Repeat MTX levels Q 12 hrs
	10-19.9 μM	6-9.9 µM	
 
Leucovorin at 15 mg/m² at Hr 42 then continue Q 3 hours until plasma MTX is < 0.1 μM
 

			Repeat MTX levels Q 12 hrs
			Consider glucarpidase
	20-200 μM	10-100 μM	
 
Leucovorin at 100 mg/m² at Hr 42 then continue q 6 hours until plasma MTX is < 0.1 μM
 

			Repeat MTX level Q 12 hrs
			Consider glucarpidase
	>200 µM	>100 µM	
 
Leucovorin at 1000 mg/m² at hr 42 and continue q 6 hours until plasma MTX is < 0.1 μM
 

			Repeat MTX level Q 12 hrs
			Consider glucarpidase

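### The per-infusion adverse event comparison can be biased by unequal follow-up, because the end of the collection window is ambiguous and the analysis sets no common window

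*Combined protocol and SAP*

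**What the plan says.** All places below are in the combined protocol and SAP.

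- **Adverse event window.** Section 5.7: "Toxicities will be assessed until the next cycle of chemotherapy is administered or until 4 weeks after the administration of HDMTX", whichever period is shorter. Section 4.2 gives the same rule. Section 7.2.2 takes patients off study at 4 weeks or at the next chemotherapy, again whichever is shorter.
- **Dosing interval.** Section 4.1, on the longest time on study: "This would include 4 doses of HDMTX given every other week plus a 4 week follow-up period to assess for side effects". Section 9.3 also refers to blocks "in which patients are administered HDMTX every 2 weeks".
- **Lab window.** Section 5.4 repeats the safety labs weekly until "either the next dose of HDMTX is administered or 4 weeks have passed since the last" dose. The footnote to the Appendix A schedule reads: "Repeat Week 2 labs weekly until the next dose of methotrexate or 30 days since last dose of methotrexate".
- **Analysis.** Section 9.1, Aim 2a: "Calculate the frequency of adverse effects after each infusion". Sections 9.1 and 9.3 extend the GEE for binary outcomes to adverse event frequency, and use a paired t-test or signed-rank test for continuous and ordinal effects. Neither section gives an offset, person-time, a time-to-event method or a common window.

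**The concern.** GEE allows for correlation between infusions in the same patient. It does not allow for one infusion being watched longer than another. The paired tests do not either, and a maximum grade can only rise as the window lengthens. Ascertainment also differs. With labs at Weeks 1 and 2 and weekly after that, an infusion followed by another dose at two weeks has two scheduled draws, while the last infusion can have four. Myelosuppression, hepatotoxicity and nephrotoxicity are largely detected by labs.

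Section 2.3.3 adds that side effects can delay later chemotherapy, so toxicity can lengthen its own observation window.

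What is at stake is how a secondary result is read. An apparent rise in toxicity at the last infusion could reflect longer observation alone and be taken for cumulative toxicity of the dosing algorithm.

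**Working it through.** **Step 1. Window lengths, and a check on the plan's own figure.** Inputs: four doses, a two-week interval and up to 4 weeks after the last dose (Section 4.1). Total time is 3 × 2 + 4 = 10 weeks, or 70 / 30.44 = 2.3 months, broadly in line with the stated maximum of 2.5 months. If the window closes at the next HDMTX dose, the four windows are about 2, 2, 2 and up to 4 weeks. The last is up to 4 / 2 = 2 times as long.

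**Step 2. What the term *cycle* means.** The text supports two readings:

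| Place | Sense of the term |
|---|---|
| Section 4.1, re-enrolment rule | one HDMTX administration |
| Section 9.1, primary endpoint tied to each patient's first cycle | one HDMTX administration |
| Section 5.4 and Appendix A, labs | stop at the next methotrexate dose |
| Section 9.3, Aim 1b | a block: "interim maintenance and interim maintenance-like cycles in which patients are administered HDMTX every 2 weeks" |

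On the single-dose reading, follow-up is unequal. On the block reading, the windows of infusions 1 to 3 run about two weeks past the following dose. An event in that overlap can then be counted for two infusions. The two problems are alternatives.

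**Step 3. Size on the single-dose reading, with no true difference.** Let p14 be the risk of at least one event in 14 days, and k the hazard in days 15 to 28 relative to days 1 to 14. Both are assumptions, because the documents give no event timing.

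- Risk over 28 days: p28 = 1 − (1 − p14)^(1 + k)
- Odds ratio: OR = [p28 / (1 − p28)] / [p14 / (1 − p14)]

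Example: p14 = 20%, k = 1. Then p28 = 1 − 0.8² = 36%, and OR = (0.36 / 0.64) / (0.20 / 0.80) = 2.25.

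| k | p14 = 10%: p28 (OR) | p14 = 20%: p28 (OR) | p14 = 40%: p28 (OR) |
|---|---|---|---|
| 0 (all events by day 14) | 10.0% (1.00) | 20.0% (1.00) | 40.0% (1.00) |
| 0.1 | 10.9% (1.11) | 21.8% (1.11) | 43.0% (1.13) |
| 0.25 | 12.3% (1.27) | 24.3% (1.29) | 47.2% (1.34) |
| 0.5 | 14.6% (1.54) | 28.4% (1.59) | 53.5% (1.73) |
| 1 (constant hazard) | 19.0% (2.11) | 36.0% (2.25) | 64.0% (2.67) |

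Odds ratios look larger than risk ratios here. Under constant hazard the risk ratio is 0.19 / 0.10 = 1.9 at p14 = 10%, and 0.64 / 0.40 = 1.6 at p14 = 40%.

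**Step 4. A shorter last window.** Four weeks is a maximum. If chemotherapy resumes 3 weeks after the last dose, constant hazard gives the exponent 3 / 2 = 1.5, so the k = 0.5 row applies (10% against 14.6%, 20% against 28.4%). If it resumes at about 2 weeks, the windows are equal and the odds ratio is 1.0.

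**Step 5. What is untouched.** The primary endpoint is the methotrexate level at the end of the 24-hour infusion. Its stated precision, 2 × 1.96 × √(0.8 × 0.2 / 50) = 0.22, involves no adverse event data.

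**The case against.** The strongest reply is that the bias is possible but not shown. Follow-up ends at 4 weeks or at the next chemotherapy, and the plan does not say when chemotherapy resumes after the last HDMTX dose. A constant hazard for 28 days after a 24-hour infusion is an extreme assumption, and the effect is small if most events come early. This stands, so the point is limited to a possible bias of unknown size.

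Second, unequal follow-up and double counting need different meanings of *cycle* and cannot both occur. That also stands. It does not clear the plan, since each reading leaves the per-infusion frequency with a problem.

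Third, a reader might infer that secondary aim 1.2.1 is invalidated, or that patients with a single study infusion will look more toxic. The documents support neither. Aim 1.2.1 asks for incidence and not for a comparison between infusions; variable follow-up there needs stating, but it is not a comparison bias. No comparison of one-infusion patients is planned. Section 4.1 lets patients take part for any one or more of their administrations, so a single study infusion may be followed by an off-study dose two weeks later.

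Fourth, equal windows do not make the last infusion comparable. Section 7.1.1 removes patients from protocol therapy for renal or neurologic toxicity of grade 3 or higher, so last study infusions can be enriched for toxicity. This stands as a limit on the remedy.

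**Conclusion.** The point holds as a possible bias in a secondary analysis. The plan compares adverse events per infusion, its rules allow windows that differ up to twofold (or overlap, on the other reading), and nothing in Sections 9.1 or 9.3 adjusts for either.

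On the single-dose reading, with no true difference, the spurious odds ratio for the last infusion lies between 1.0 and about 2.7. Values of 2.1 to 2.7 require both a constant hazard and a full 28-day last window, at a 14-day risk of 10% to 40%. With a late hazard of a tenth to half of the early one, the range is about 1.1 to 1.7. The documents do not allow a choice within these ranges.

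It would be tempting to say that the comparison *is* biased, or that the trial's main result is in doubt. The documents support neither: 4 weeks is only an upper limit, and the primary endpoint is fixed at 24 hours.

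**What to change.** 1. **Sections 9.1 (Aim 2a) and 9.3.** Compare adverse event frequency and maximum grade between infusions over one common window: start of infusion to day 14 or the next HDMTX dose, whichever is first. Report later events separately and in the overall incidence table, and state there that follow-up length varies.
2. **Sections 4.2, 5.4, 5.7, 7.2.2 and Appendix A.** Use one end-of-window definition for attributing events: the next HDMTX dose or the next chemotherapy cycle, whichever is first, up to 4 weeks. Reconcile the 4 weeks in Section 5.4 with the 30 days in Appendix A. Each event then belongs to one infusion.
3. **Section 5.7.** Make the onset date a required item for every collected adverse event. At present, start dates appear only as an example of other information to be listed.
4. **Interpretation.** State that any trend over infusions is descriptive, because the common window does not remove the selection created by Section 7.1.1.

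The cost is wording in the protocol and SAP plus one required data item. No visit, sample or treatment changes. The downside is that events after day 14 leave the between-infusion comparison, though they remain in the incidence table.

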### 6. DRUG INFORMATION

See the consent document for toxicities. All other information is available on the COG website in the manual titled —Drug Information for Commercial Agents used by the Children's Oncology Group https://members.childrensoncologygroup.org/prot/reference\_materials.asp under Standard Sections for Protocols. Also see drug package inserts for added information on toxicities.

Protocol Version 8.0 Date: June 17, 2015

#### 7. CRITERIA FOR REMOVAL FROM PROTOCOL THERAPY AND OFF STUDY CRITERIA

- 7.1 Removal from Protocol Therapy
  - 7.1.1 ≥ Grade 3 renal or neurologic toxicity
  - 7.1.2 Parent/patient or provider request
  - 7.1.3 Inability to analyze methotrexate levels at given time points. Patients will come off of study secondary to the inability to make dose modification decisions if methotrexate levels at required time points are not available within 120 minutes of drawing the level. If this occurs, treatment decisions will be up to the treating physician. Options would include: discontinuing the methotrexate infusion, altogether or calculating a 25% total dose reduction (as suggested by COG) and stopping the infusion when the total dose given reaches the newly calculated reduced dose.
  - 7.1.4 Methotrexate infusion interrupted for longer than 2 hours.
- 7.2 Off Study Criteria
  - 7.2.1 Lost to follow-up
  - 7.2.2 4 weeks after the end of methotrexate infusion or start of next chemotherapy, which ever is shorter.
  - 7.2.3 Death
- 8. Data Monitoring

Texas Children's Cancer Center, where we will be conducting our research, is part of the Dan L. Duncan Cancer Center (DLDCC). The NCI-designated Dan L. Duncan Cancer Center at Baylor College of Medicine is a consortium made up of several institutions across the Texas Medical Center. As part of the DLDCC, we will have access to various shared resources, including a Clinical Trials Support Unit. For our data monitoring, we will utilize the Data Safety and Monitoring Committee (DSMC) through the DLDCC.

- 8.1. Stopping rules
  - 8.1.1. Two patients with HDMTX induced nephropathy necessitating dialysis or administration of carboxypeptidase.
  - 8.1.2. Two patients achieving a 24 hour  $Cp_{ss}$  of <20 $\mu$ M.
  - 8.1.3. Two patients needing intensive care admission for HDMTX related toxicities.
  - 8.1.4. Any death attributed to HDMTX toxicity.

If any of the above criteria are met then the study will be stopped, the incident(s) will be reviewed, and the study will be amended to address the incident(s) prior to potentially re-opening.

- 9. Statistical Considerations
- 9.1 Statistical Design

Aim 1 1a) Calculate the incidence of success with the new protocol (achieving an end infusion

Protocol Version 8.0 Date: June 17, 2015

peripheral blood MTX concentration between 50-80 μM)

- 1b) Explore potential changes in incidence of success (achieving an end infusion peripheral blood MTX concentration between 50-80  $\mu$ M) between sequential administrations of HDMTX. The primary endpoint and sample size calculation refer to the first cycle for each patient.
- Aim 2 2a) Calculate the frequency of adverse effects after each infusion. Success rate over multiple cycles within individual patients will be analyzed using generalized estimating equations for binary outcomes. This method will also be applied to the frequency of adverse events and to the assessment of factors associated with outcome. Continuous and ordinal/non-normal adverse effects will be compared via paired t-test or Wilcox sign rank test respectively.
- 2b) Describe the genotype of various methotrexate metabolizing SNPs in each subject. The polymorphisms of subjects in this study will be compared to published minor allele frequencies and when appropriate will be stratified by race/ethnicity. The purpose of this analysis will be to describe trends away from the major allele frequency in patients known to either have experienced or who are at high risk for developing adverse effects to HDMTX.
- 2c) Examine predictors of success of achieving a  $CP_{ss}$  of 50-80  $\mu$ M. Variables in our analysis will include (but not be limited to) age, sex, disease type, race/ethnicity and measure of pre-MTX renal function. An analysis both with and without SNP genotype will be performed secondary to the likelihood that race/SNP correlations will interfere with SNPs being a truly independent variable. We will initially use chi-square test for group variables and t-test for continuous variables. Logistic regression will be used for multivariable analysis to control for confounders and estimation of adjusted odds ratios. P<0.05 will be considered statistically significant.

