### B. Interventions at 6 hours (\*8 hours if 2 hour level was ≥100µM)

If MTX level is:	<75μM	≥75µM/<100µM	≥100µM
MTX administration intervention	·Continue Unchanged	·Reduce MTX infusion 20% from MOST RECENT infusion rate; Therefore, if (select A OR B): A) 2 hr MTX level was <100 μM and therefore, infusion rate was 200 mL/m²/hr then restart at 160 mL/m²/hr B) 2 hr MTX level was ≥100 μM and therefore, infusion rate was 100 mL/m²/hr then restart at 80 mL/m²/hr	·Stop infusion for 1 hour ·At restart time; restart MTX at 50% reduction from MOST RECENT infusion rate; Therefore, if (select A OR B): A) 2 hr MTX level was <100 µM and therefore, infusion rate was 200 mL/m²/hr then restart at 100 mL/m2/hr B) 2 hr MTX level was ≥100 µM and therefore, infusion rate was 100 mL/m²/hr then restart at 50 mL/m²/hr
Fluid intervention	·Continue unchanged	Select A OR B: A) If 2 hr MTX level was <100 µM and therefore, there was no previous additional fluid order then begin D5 ¼ NS with NaHCO3 3 mEq/100 mL at 40 mL/m²/hr B) If 2 hr MTX level was ≥100 µM and therefore, additional D5 ¼ NS with NaHCO3 3 mEq/100 mL was already running at 63.5 mL/m²/hr then increase this fluid to run at 120 mL/m²/hr	Select A OR B A) If 2 hr MTX level was <100 µM and therefore, there was no previous additional fluid order then begin D5 ¼ NS with NaHCO3 3 mEq/100 mL at 100 mL/m²/hr B) If 2 hr MTX level was ≥100 µM and therefore, additional D5 ¼ NS with NaHCO3 3 mEq/100 mL was already running at 100 mL/m²/hr then increase this fluid to run at 150 mL/m²/hr

MTX level	·Check MTX level	·Check MTX level again at 24,	·Check MTX level again at 24,
specific lab	again at 24, 36, 42	36, 42 and 48 hours per COG	36, 42 and 48 hours per COG
instructions	and 48 hours per	algorithm#	algorithm#
	COG algorithm#		_

\*see COG algorithm on page 21

Subjects will come off protocol therapy for infusion delays longer than 2 hours. In addition, the total methotrexate infusion time, on this study, should be no longer than 26 hours. Infusions should only be extended past 24 hours to accommodate stops for other med infusions. Increases in rate of MTX infusion to ensure completion within this time frame are **not** allowed.

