### 4.2 Study Endpoints

After the initial monitoring of MTX levels and creatinine during the MTX infusion, patients will be followed for the development of HDMTX related toxicity for 4 weeks after their infusion or until their next cycle of chemotherapy begins, whichever is shorter.

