#### 9.2 Patient Accrual and Expected Duration of Trial

Patients will be continually accrued until a target of 50 methotrexate infusions requiring any protocolprescribed dose adjustments are reached. The expected duration of accrual for the trial is 2-2.5 years.

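### Section 7.1.3 sends patients with a late methotrexate level off study under a heading about leaving protocol therapy; read literally, this ends required collection of toxicity data and, after a late 2-hour or 6/8-hour result, of the 24-hour level

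*Combined protocol and SAP*

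**What the plan says.** Section 7 separates two statuses: removal from protocol therapy (7.1) and going off study (7.2). Item 7.1.3 is in the first list. It covers a required methotrexate level that is not available within 120 minutes of the draw, and it states: "Patients will come off of study secondary to the inability to make dose modification decisions". Treatment is then left to the treating physician, and the options named include ending the infusion.

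Section 7.2 gives three off-study criteria: loss to follow-up, reaching 4 weeks or the next chemotherapy, and death.

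Other sections bear on the same patients:

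- Section 4.1, below table B, has a rule for a different trigger: "Subjects will come off protocol therapy for infusion delays longer than 2 hours". It does not mention leaving the study.
- Section 4.1 also says that patients who have finished the 24-hour infusion are off protocol therapy but still on study. On duration it says: "The active length of study participation for each patient is 4 weeks after the last high-dose methotrexate infusion", or until the next cycle if that is sooner.
- Section 5.4: "Methotrexate levels and creatinine at times 2, 6 (or 8) and 24 hours are required for research purposes". It also schedules weekly laboratory tests.
- Section 4.2: "patients will be followed for the development of HDMTX related toxicity for 4 weeks after their infusion", with the next cycle as the earlier limit. Section 5.7 agrees: "Toxicities will be assessed until the next cycle of chemotherapy is administered or until 4 weeks after the administration of HDMTX".

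None of these follow-up passages makes an exception for a late level. Section 9 does not say how an infusion removed under 7.1 enters the primary analysis.

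**The concern.** Site staff act on the wording in front of them. A coordinator who reads 7.1.3 and takes a patient off study after a late 2-hour or 6/8-hour result has no remaining protocol requirement to record the 24-hour level, the weekly laboratory tests or the graded toxicities. The 24-hour level is the basis of the primary aim (Section 1.1). The toxicities are the subject of aim 1.2.1, which covers high-risk patients receiving the infusion and is not limited to those who complete the algorithm.

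Infusions that leave the algorithm would then differ from the rest in how much is known about them. A later choice of analysis cannot restore data that were not collected.

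**Working it through.** **Step 1: the texts side by side.**

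| Place | Trigger | Status given |
|---|---|---|
| 7.1 heading | all items below it | off protocol therapy |
| 7.1.3 text | level not available within 120 minutes | off study |
| 7.1.1, 7.1.2, 7.1.4 | grade 3 or higher renal or neurologic toxicity; request; interruption over 2 hours | no off-study wording |
| 7.2 | three criteria, none of them a late level | off study |
| 4.1, below table B | infusion delay over 2 hours | off protocol therapy |
| 4.1, after the infusion | infusion complete | off protocol therapy, on study |

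The direct contradiction is inside Section 7: 7.1.3 against its own heading and against 7.2. The two Section 4.1 rules concern other triggers. They show that the protocol keeps the statuses apart, but they are not a second rule for late levels.

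**Step 2: what a literal reading removes.**

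- Late 2-hour or 6/8-hour result: required study collection of the 24-hour level, the weekly tests and the toxicity grades.
- Late 24-hour result: the sample is already drawn, so only follow-up and the use of the value are in question.

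**Step 3: the plan's own precision figure.** Section 9.3 gives n = 50, an assumed proportion of 0.80 and a two-sided 95% interval. The half-width is 1.96 × √(0.80 × 0.20 / 50) = 0.111. The interval is 0.689 to 0.911 and its width is 0.222. This reproduces the stated 0.22 and 69% to 91%.

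**Step 4: illustration of the effect.** Suppose m of 50 started infusions are removed without a 24-hour level, and 80% of the others succeed. Both m and the 80% are assumptions. The all-started rate then runs from 0.80 × (50 − m)/50, if every removed infusion counts as a failure, to [0.80 × (50 − m) + m]/50, if every one counts as a success. The width of the range is m/50.

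- m = 1: width 1/50 = 2 points.
- m = 5: 36 of 45 succeed; from 36/50 = 72% to 41/50 = 82%; width 10 points.
- m = 10: 32 of 40 succeed; from 32/50 = 64% to 42/50 = 84%; width 20 points.

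The completers-only rate is 80% in each case. At m = 5 it is therefore 8 points above the lower end and 2 points below the upper end.

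**Step 5: loss of precision.** With 45 infusions the half-width is 1.96 × √(0.16/45) = 0.117, against 0.111 with 50. That is a small change. How the removed infusions are counted matters more.

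**The case against.** **It is probably a slip.** The sentence gives as its reason that dose decisions cannot be made, which is a reason to end protocol therapy. The heading and Section 7.2 point the same way, and no passage states that data collection stops. This stands. The inconsistency is certain; the data loss is an inference from the literal words.

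**The 24-hour value may exist anyway.** Tables A and B in Section 4.1 list a 24-hour level under the cooperative-group algorithm, and Section 5.6 collects all levels resulted. This stands in part: a clinical value might be available, but nothing requires it as study data once the patient is off study.

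**The all-started rate can still be calculated.** A reader might infer that the missing levels make it impossible to obtain. They do not. If removed infusions count as failures the rate is fixed, 36/50 in the example, and a completers-only rate never needs those levels. The gap is that no counting rule is written.

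**Collecting the level may not settle the matter.** If the physician ends the infusion early, a 24-hour sample may not be the end-infusion concentration that Section 9.1 defines as success. This stands.

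**The size is hypothetical.** No late-level rate is reported, and a late result may reflect nothing more than laboratory turnaround. Section 9.2 accrues to a number of infusions that needed an adjustment, so removed infusions might also be replaced, in which case the loss of precision would not arise. This stands, and the figures are offered only as an illustration.

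**Conclusion.** The concern holds as an internal contradiction with a plausible cost in data. Section 7.1.3 conflicts with its own heading and with 7.2, and it departs from the usage in Section 4.1. Read literally, it ends required collection of toxicity data and, after a late 2-hour or 6/8-hour result, of the 24-hour level. Section 9 leaves the counting of these infusions open.

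The size depends on an undocumented removal rate: 2 points of uncertainty in the all-started rate with 1 of 50 removed, and 10 points (72% to 82%) with 5 of 50, assuming 80% success in the rest and no 24-hour level in those removed.

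A reader might also infer that the plan excludes late-level infusions from the primary analysis, or that the reported success rate would be too high. The documents support neither. No passage excludes these infusions, and nothing links late results to outcome, so the direction of any bias is not established.

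**What to change.** - **Section 7.1.3.** Reconcile it with 7.2 and 4.1, so that a patient with a late level leaves protocol therapy but stays on study for the 24-hour level and the toxicity follow-up already scheduled.
- **Section 9, reporting.** State the number of removed infusions, with reasons.
- **Section 9, success rate.** Give it in two ways: over all started first infusions, and for completers only. The first-infusion basis follows Section 9.1: "The primary endpoint and sample size calculation refer to the first cycle for each patient". In the all-started rate, count as failures either all removed infusions or those with no valid end-infusion level. Write that choice down before the data are examined, and say how a sample taken after an early stop is treated.

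The cost is a change of wording and a short paragraph. No procedure is added. The clinical options listed in 7.1.3 are not touched, and no management rule is proposed.

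Two related matters are separate and need not delay this change: how the stopping rule in 8.1.2 treats levels after a shortened infusion, and the difference between the first-cycle basis in 9.1 and the accrual target in 9.2.
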